3.2 Part B

This will be an open-label, randomized phase II study that will compare the safety and efficacy of CC-486 and pembrolizumab (using the schedule that was established as optimal in Part A) with pembrolizumab alone, for the treatment of platinum-resistant/refractory EOC.

If necessary, a protocol amendment may be released to further define the eligibility criteria, treatment schema, etc. for Part B, based on the analysis of Part A. If there are no changes in the study design, conduct, treatments, safety consideration, etc., this same protocol version will be used for both Part A and Part B.

Eligible subjects will be randomly assigned in a 1:1 ratio to either:

- Arm A: Pembrolizumab (200 mg IV every 21 days) in combination with CC-486 (dosing schedule established in Part A)

or

- Arm B: Pembrolizumab (200 mg IV every 21 days) as a single agent

A total of 150 subjects, 75 per arm, will be randomized over an estimated period of 24 months. To ensure equal distribution of prognostic factors in the two study arms, subjects will be stratified according to the following parameters:

- Type of relapsed disease: platinum-refractory vs. platinum-resistant (refer to the corresponding definitions in section 4.1)
- Prior treatment regimens for the platinum-refractory/resistant EOC: none vs. 1 or 2

Subjects with tumor lesions amenable to core biopsy will be proposed (although not mandated) to undergo image-guided core biopsy at study entry and 6 weeks (\pm 1 week) after first dose of study treatment, provided that the tumor lesion is amenable to a second biopsy.

Subjects will be treated until progressive disease based on irRECIST, unacceptable toxicity, consent withdrawal or the Investigator concludes that it is in the subject's best interest to discontinue (or any other withdrawal criteria is met according to section 5.5). Once the subject is discontinued from study treatment and has undergone the End of Treatment visit, she will enter into the follow-up phase. Subjects who discontinue treatment for reasons different than progressive disease will continue to be

followed with tumor assessment every 12 weeks until irPD. After progressive disease, subjects will be followed for assessment of survival status every 6 months (visit or phone contact) until death or for at least 1 year after the End of Treatment visit.

Part B also includes an optional exploratory research component (see section 6.4.7).

[figure not shown]

Figure 3: Study schema

3.3 Part A: Determination of the Optimal Schedule for Part B

The optimal schedule to be used in Part B will be selected after analysis of the accumulated safety and efficacy data from Part A by the Steering Committee. The analyses will be conducted once 5 subjects in each cohort are considered evaluable. Subjects will be considered evaluable once they have:

- Completed at least two CC-486 cycles
- Undergone the 1st post-baseline tumor burden assessment
- Undergone the 2nd tumor biopsy and adequate paired tissue obtained

Full details of the criteria to be used to guide the Steering Committee in their selection of the optimal regimen will be described in the Steering Committee Charter. In general, however, the following decision criteria will be applied:

- Step 1: Safety and Futility evaluation:

A cohort will be rejected due to toxicity if any of the below criteria is met:

- One grade 5 AE related to study drugs
- More than one subject experiencing a grade 4 AE related to study drugs (other than hypothyroidism)

- More than 2 subjects experiencing a grade 3 AE related to study drugs (other than hypothyroidism)

A cohort will be rejected due to futility if at least one response or stable disease (irPR, irCR or irSD) is not observed in that schedule.

- Step 2: Determination of the optimal schedule: In the cohort(s) not rejected due to toxicity or due to futility, the selection by the Steering Committee of the optimal schedule will be based on the toxicity profile and the irORR of each cohort (irDCR may also be considered for the determination of the optimal schedule). For example, if one cohort has higher irORR and similar toxicity profile compared to another cohort, the first one will be selected as optimal. If two or more cohorts have the same irORR, the optimal schedule will be established based primarily on the more favorable toxicity profile. Additionally, data from the correlative analyses to be done in the biologic samples described in section 6.4.7, may be taken into consideration for determining the optimal schedule.

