3.1 Part A

Part A is an open-label, four-cohort, non-randomized, lead-in selection phase in which intravenous (IV) pembrolizumab will be combined with 4 different schedules of administration of oral CC-486, for the treatment of platinum-resistant/refractory EOC. Part A is also a futility trial for the strategy to combine pembrolizumab and CC-486 in EOC.

Eligible subjects will be treated in one of four cohorts of combined oral CC-486 and pembrolizumab (200 mg IV q3 weeks in all cohorts) (refer to section 5.3.3 for details on study treatments administration) to evaluate the safety of each combination schedule and to have preliminary data on their efficacy. The primary objective of Part A is to establish the optimal dosing schedule for comparison with pembrolizumab alone in Part B of the study.

Subjects will be assigned to a treatment cohort in the order they are enrolled in the study (e.g. first subject in cohort 1, second subject in cohort 2, etc.). In all subjects, tumor tissue will be obtained via image-guided core biopsy at study entry and 6 weeks after commencing treatment with CC-486, provided that the tumor lesion is amenable to a second biopsy. A cohort will remain open to accrual until five subjects treated on that cohort have completed two CC-486 cycles and have had the first post-baseline tumor burden assessment and both tumor biopsies performed and adequate paired tissue obtained. If a subject assigned to a given cohort is not evaluable (i.e. have not completed two CC-486 cycles and/or have not had the first post-baseline tumor assessment and/or both tumor biopsies) then these subjects will be replaced. At least 5 evaluable subjects per cohort will be accrued to Part A over an estimated period of approximately 24 months.

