Subjects will be treated in the assigned cohort until progressive disease based on irRECIST, unacceptable toxicity, consent withdrawal or the Investigator concludes that it is in the subject's best interest to discontinue (or any other withdrawal criteria is met according to section 5.5). Subjects who discontinue treatment for reasons different than irPD will enter the follow-up phase and will continue to be followed with tumor assessment every 12 weeks until irPD. After irPD, and provided that subject has undergone the End of Treatment visit, all subjects will be taken off the study unless presence of serious adverse events (SAEs) or study treatment-related adverse events. In such case these events will be monitored as clinically indicated until the events have resolved (or return to baseline) or in the Investigator's opinion, are unlikely to resolve due to the nature of the condition and/or the subject's underlying disease.

Once 5 subjects in each cohort are considered evaluable, enrollment will be stopped and data from each cohort will be analyzed and the optimal schedule to be taken forward into Part B will be selected according to section 3.3.

Part A includes mandatory tumor core biopsies for biomarkers research and mandatory whole blood sampling for DNA methylation analyses (see section 6.4.7).

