6.1.2 Registration, Enrollment/Randomization and Treatment Assignment

6.1.2.1 Part A

The following steps for registering and enrolling a subject are chronologically performed:

1. The subject must provide written informed consent prior to performing any study specific procedure not considered standard practice by the institution.
2. The site will ask TRIO for subject's registration immediately after signature of PICF. A unique registration number will be assigned to each subject in the study.
3. The site will proceed to perform the screening procedures according to the Schedule of Assessments and section 6.4. Upon completion of screening procedures, the Investigator or his/her delegate will check if the subject meets all eligibility criteria:
 - Subjects who do not meet all eligibility criteria: sites will have the screen failure form completed in the eCRF with corresponding reason for screen failure captured.
 - Subjects who meet all eligibility criteria: sites will enter the screening data in the eCRF which will be reviewed centrally by TRIO. After the review of the eligibility criteria, TRIO may address, if necessary, some discrepancies that will have to be answered by the site. Once the eligibility central review is completed and discrepancies have been resolved (if applicable) TRIO will provide the confirmation that the subject is eligible and the site will be able to move forward with the subject's enrollment in the eCRF. The site will receive a confirmation of enrollment. If the subject is deemed not eligible following the central eligibility review, the site will be asked to report the screen failure reason in the eCRF.
4. Subjects will be assigned to a cohort in the order they are enrolled in the study. Subjects enrolled in Part A must start study treatment within 3 days of enrollment.

A cohort will remain open to accrual until five subjects treated on that schedule are considered evaluable as per the definition in section 3.3 (subject completed at least 2 CC-486 cycles and have undergone the 1st post-baseline tumor burden assessment and the 2nd tumor biopsy). It is critical that data about the tumor biopsies and 1st tumor burden assessment is entered by the sites in the eCRF in a

timely manner since this is required to close accrual for the corresponding cohort also in a timely manner. TRIO will also review the tumor collection and tumor assessments data and closely follow-up the performance of these procedures.

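### Part A's toxicity rejection criteria cannot be un-met, yet a cohort that has met one stays open to accrual until its own five subjects are evaluable

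*Protocol*

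**What the plan says.** **Rejection.** Step 1 of Protocol section 3.3 states: "A cohort will be rejected due to toxicity if any of the below criteria is met". The limits are "One grade 5 AE related to study drugs", more than one subject with a related grade 4 event, and more than two subjects with a related grade 3 event (hypothyroidism is excepted from the last two). The section does not say whether the counts cover all treated subjects or only evaluable ones.

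**When the criteria are applied.** Section 3.3 says: "The analyses will be conducted once 5 subjects in each cohort are considered evaluable". Section 3.1 agrees: "Once 5 subjects in each cohort are considered evaluable, enrollment will be stopped and data from each cohort will be analyzed". Protocol 8.8 and SAP 2.4 give the same timing.

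**When a cohort closes.** Section 3.1: "A cohort will remain open to accrual until five subjects treated on that cohort have completed two CC-486 cycles", together with the first post-baseline tumor assessment and adequate paired biopsies. Section 6.1.2.1: "A cohort will remain open to accrual until five subjects treated on that schedule are considered evaluable". Neither has a toxicity exception. For subjects who do not become evaluable, section 3.1 says "then these subjects will be replaced".

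**Oversight.** Section 9.1 gives the Steering Committee a general duty to monitor accrual, compliance and safety. Section 3.3 leaves the full selection criteria to the Committee's Charter, which is not among the documents.

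**The concern.** The three criteria are absolute counts. Later subjects without toxicity cannot bring a count back down, so a cohort's rejection can be settled well before its fifth evaluable subject. The accrual rules do not respond to that. Anyone who follows sections 3.1 and 6.1.2.1 exactly will keep assigning subjects to a schedule that section 3.3 says will be rejected.

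Replacement adds to this. Under section 5.7.3.3 a life-threatening adverse reaction ends CC-486, and under section 5.5 stopping one drug stops both. If that happens before two cycles are complete, the subject is not evaluable and another is enrolled in the same cohort. The toxicity that settles the rejection can therefore itself bring in a further subject.

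At stake is avoidable exposure to a schedule that cannot go forward, including two mandatory core biopsies for each added subject.

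**Working it through.** **Plan's own figure.** SAP 2.3 gives a minimum of 20 subjects: 4 cohorts × 5 = 20, which reproduces. Protocol 8.7 states that Part A has no formal sample size calculation, so there is no power or alpha to check.

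**One case with no assumed rate.** If a cohort's first subject has a related grade 5 event, the first limit is met at once. At least 4 more subjects must still be enrolled. If the death comes before the subject is evaluable, it is 5 more.

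**Each criterion alone.** Assumptions: five subjects, no replacement, independent outcomes, and each outcome known before the next subject enters that cohort. With per-subject rate p:

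- Grade 4 limit (two affected) met before the fifth subject: P(Bin(4,p) ≥ 2) = 1 − (1−p)^4 − 4p(1−p)^3
- Grade 3 limit (three affected) met before the fifth subject: P(Bin(4,p) ≥ 3) = 4p^3(1−p) + p^4
- Mean subjects enrolled after the limit is met: the sum over m = 1 to 4 of P(limit met by subject m)

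| Criterion | Assumed p | Met before fifth subject | Mean later subjects |
|---|---|---|---|
| Grade 4 | 0.20 | 1 − 0.4096 − 0.4096 = 18.1% | 0.04 + 0.104 + 0.1808 = 0.32 |
| Grade 4 | 0.30 | 1 − 0.2401 − 0.4116 = 34.8% | 0.09 + 0.216 + 0.3483 = 0.65 |
| Grade 3 | 0.20 | 0.0256 + 0.0016 = 2.7% | 0.008 + 0.0272 = 0.04 |
| Grade 3 | 0.30 | 0.0756 + 0.0081 = 8.4% | 0.027 + 0.0837 = 0.11 |
| Grade 3 | 0.50 | 0.2500 + 0.0625 = 31.3% | 0.125 + 0.3125 = 0.44 |
| Grade 3 | 0.60 | 0.3456 + 0.1296 = 47.5% | 0.216 + 0.4752 = 0.69 |

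**All three criteria together.** Subjects are classed by worst related grade. The no-replacement columns are exact enumeration over five subjects. The replacement columns come from 100,000 simulated cohorts, assuming non-evaluability of 100% after grade 5, 30% after grade 3–4 and 20% otherwise.

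| Assumed grade 5/4/3 rates | Any later enrolment, no replacement | Mean later subjects | Any later enrolment, with replacement | Mean later subjects |
|---|---|---|---|---|
| 1/5/20% | 8.0% | 0.16 | 17.6% | 0.52 |
| 2/10/30% | 20.9% | 0.39 | 40.9% | 1.26 |
| 2/20/40% | 42.4% | 0.75 | 68.7% | 2.23 |

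**Could the criteria be checked during accrual?** Section 3.1 plans about 24 months and assigns subjects to cohorts in order of enrolment. With 20 subjects, a cohort receives one about every 24/20 × 4 = 4.8 months. With 32 subjects it would be 24/32 × 4 = 3.0 months. Two 28-day cycles take 56/30.4375 = 1.84 months. At the planned pace, toxicity from the first two cycles would usually be known before that cohort's next subject enters.

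**The case against.** **The Charter and section 9.1.** The Committee already monitors accrual and safety, section 3.3 introduces its criteria only as a general guide, and the Charter may contain an early-closure rule. This stands in part. A reader might infer that no such rule exists anywhere, and the documents cannot show that. But section 9.1 does not link these criteria to accrual. Section 3.3 points to the Charter for choosing the regimen. Sites enrol under the protocol, whose text would still have to agree with any Charter rule. The sponsor's right to terminate (3.5) concerns the whole trial.

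**Selection thresholds, with protection elsewhere.** Individual subjects are covered by holding, reduction and discontinuation rules (5.5, 5.7). A reader might infer that subjects are left unprotected, and that is not so. The narrower point remains that those rules do not govern whether new subjects enter.

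**Later subjects still inform.** It is tempting to say they contribute nothing. Section 3.3 allows correlative data into the choice of schedule, and Part A is also a futility trial of the combination strategy, so that goes too far. What they cannot do is make a rejected schedule selectable.

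**Duration.** It is also tempting to read accrual as running until all four cohorts are full. Sections 3.1 and 6.1.2.1 close each cohort at its own five evaluable subjects. Only the analysis waits for all four.

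**Size.** The protocol describes pembrolizumab events as mostly low grade (1.3.2) and expects CC-486 up to 300 mg daily to be well tolerated (1.4.2). Grade 3 rates of 50–60% therefore should not be quoted without the 2.7–8.4% that follows from rates of 20–30%. In addition, a running count cannot prevent enrolments made before a late-cycle toxicity appears.

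**Conclusion.** The point holds on the text. Sections 3.1 and 6.1.2.1 keep open a cohort that section 3.3 says will be rejected, and nothing in the documents reconciles them. This conclusion needs no assumed rate.

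The size does depend on assumed rates. For each criterion alone, without replacement, the mean excess is 0.04 to 0.69 subjects per cohort. With the criteria combined and replacement at the assumed non-evaluability rates, it is 0.52 to 2.23. All of these figures assume that each toxicity is known before the next subject enters that cohort. The numbers are small in absolute terms, but the exposure is avoidable and the criteria needed to limit it are already written. The one open question is whether the Charter provides for it. If it does, the remaining task is to bring the protocol's accrual text into line.

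**What to change.** 1. In Protocol 3.1, 3.3 and 6.1.2.1, state that the existing Step 1 toxicity criteria, unchanged, are counted on the Safety population as data accrue, and that accrual to a cohort meeting one is paused for Steering Committee review. Naming the population also ensures that a subject who dies or stops before two cycles is counted. A pause for review, rather than automatic closure, keeps the discretion that section 3.3 gives the Committee.
2. Reword the analysis trigger in Protocol 3.1, 3.3 and 8.8 and SAP 2.4 to five evaluable subjects in each cohort not already rejected for toxicity. Adjust the minimum numbers in Protocol 3.4 and SAP 2.3 to match. Without this, a paused cohort that stays below five would mean the trigger is never met. Futility and Step 2 keep the five-evaluable requirement for the remaining cohorts.
3. Align the synopsis and the Charter, say how the enrolment order skips a paused cohort, and say what follows if all four cohorts are rejected.

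No threshold, dose or individual treatment rule changes. The cost is edits in several sections, the SAP and the Charter, timely review of related grade 3–5 events, and fewer paired biopsy and methylation samples from a rejected cohort. No stated power is lost, because Part A has none.

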3.4 Number of Subjects and Investigational Sites

In Part A, at least 5 evaluable subjects per cohort will be included in the study, from 4 participating sites from the USA.

In Part B, 150 subjects will be included, from approximately 25 participating sites from the USA and Germany. The sites participating in Part A will also be participating in Part B.

3.5 Study End

The study will end once the last subject undergoes the last visit and all events required for the final analyses have been observed and collected.

The trial may be prematurely terminated by the sponsor. In this case, subjects deriving clinical benefit from the study treatment at time of trial termination will continue to be provided with study drug by the sponsor/manufacturer.

4. SUBJECT SELECTION

This study can fulfill its objectives only if appropriate subjects are enrolled. The following eligibility criteria are applicable both for Part A and B of the study.

Subjects who fail to meet all inclusion criteria or fulfill at least one exclusion criteria cannot be enrolled in the study. The sponsor will not grant any eligibility waivers. If a subject that does not meet the eligibility criteria is incorrectly enrolled in Part A or randomized in Part B, the Investigator should immediately inform the Medical Monitor. The decision about the continuation or discontinuation of these subjects on the study will be based on medical judgment, treatment benefit and safety risks for the subject.

4.1 Inclusion Criteria

1. Signed and dated informed consent document obtained prior to initiation of any study-specific procedure and treatment (by the subject or a legally acceptable representative as per the local regulations).
2. Women \geq 18 years old.
3. Histologically confirmed EOC, FTC or PPC.

4. Received debulking surgery and preoperative and/or postoperative platinum-based frontline chemotherapy (intravenous and/or intraperitoneal) for the treatment of EOC/FTC/PPC.
5. Documented platinum-resistant or platinum-refractory disease. Platinum-resistant disease is defined as progression within < 6 months from completion of a minimum of 4 platinum frontline therapy cycles in the pre or postoperative setting (the date should be calculated from the last administered dose of platinum agent). Platinum-refractory is defined as disease that has recurred/progressed while receiving platinum-based frontline therapy.
6. Measurable disease according to irRECIST for Part A. For Part B, subjects must have either measurable and/or non-measurable disease according to irRECIST (Appendix 2).
7. Indication of systemic treatment for the relapsed EOC, FTC or PPC.
8. For Part A, subjects must have a tumor lesion that is amenable to an image-guided core biopsy and willingness to undergo two biopsies (baseline and 6 weeks after first dose of study treatment). For Part B, subjects will be eligible even if their disease is not amenable to biopsy and/or the subject does not consent to the optional biopsies.
9. Eastern Cooperative Oncology Group (ECOG) Performance Status (PS) 0 or 1 (Appendix 1).
10. Expected survival of more than 6 months.
11. Adequate organ function within 7 days prior to enrollment in Part A or randomization in Part B, as defined by the following criteria:
 - Absolute neutrophils count (ANC) $\geq 1.5 \times 10^9/L$, platelets $\geq 100 \times 10^9/L$, hemoglobin > 9 g/dL (without transfusion or erythropoiesis stimulating agents' dependency).
 - Serum creatinine $\leq 1.5 \times$ upper limit of normal (ULN).
 - Total serum bilirubin $\leq 1.5 \times$ ULN regardless of liver involvement secondary to tumor. Higher levels are acceptable if these can be attributed to active hemolysis or ineffective erythropoiesis.
 - Serum aspartate transaminase (AST) and serum alanine transaminase (ALT) $< 2.0 \times$ ULN or $\leq 5 \times$ ULN for subjects with liver metastases.
 - International Normalized Ratio (INR) or Prothrombin Time (PT) $\leq 1.5 \times$ ULN unless subject is receiving anticoagulant therapy as long as PT or PTT is within therapeutic range of intended use of anticoagulants
 - Partial Thromboplastin Time (PTT) or Activated Partial Thromboplastin Time (aPTT) ≤ 40 seconds unless subject is receiving anticoagulant therapy as long as PT or PTT is within therapeutic range of intended use of anticoagulants
12. For women of childbearing potential*, negative serum pregnancy test within 7 days of enrollment in Part A or randomization in Part B.
13. Women of childbearing potential* must agree to use acceptable methods of birth control starting with the screening visit and up to 120 days after the last dose of study treatment. Recommendation is for 2 effective contraceptive methods during the study. Adequate forms of contraception are double-barrier methods (condoms with spermicidal jelly or foam and diaphragm with spermicidal jelly or foam), oral depo-provera, or injectable contraceptives, intrauterine devices, and tubal ligation.

14. Willingness and ability to comply with scheduled visits, treatment plan, laboratory tests, and other trial procedures.

** Note: Given the patient population in the trial, it is highly unlikely that women of childbearing potential (WoCBP) are enrolled. WoCBP are any women between menarche and menopause who have not been permanently or surgically sterilized and are capable of procreation. Permanent sterilization includes hysterectomy and/or bilateral oophorectomy and/or bilateral salpingectomy but excludes bilateral tubal ligation/occlusion. Non-sterile women will be considered of WoCBP if they did not have at least 12 months with no menses without an alternative medical cause.*

